5.6 Follow-Up Assessments after Adjuvant Therapy

Follow-up assessments will be planned at the following time points; actual follow up times may vary due to patient logistics and compliance:

- 6 weeks (+/- 1 week) following completion of adjuvant therapy
- 4 months (+/- 2 weeks) following completion of adjuvant therapy
- 6, 12, 18, 24, 30, 36, 48, and 60 months (+/- 6 weeks) following completion of adjuvant therapy
- annually thereafter for 5 years (total follow-up 10 years)

Patients with disease progression will only be followed for survival and will not stay on the above follow-up schedule. Their follow-up schedules will then be at the discretion of the investigator.

5.6.1 Six Week (+/- 1 week) Assessment

1. Physical examination and weight (kg).
2. Serum creatinine (BMP).
3. Documentation of ECOG performance status.
4. Documentation of narcotic and PEG tube usage.
5. Documentation of patient symptoms using NCI-CTCAE version 4.0.
6. Completion of QOL questionnaires
7. CT Neck.
8. OPTIONAL: Speech and swallowing assessment

5.6.2 Four Month (+/- 2 weeks) Assessment

1. Physical examination and weight (kg).
2. Documentation of ECOG performance status.
3. Documentation of narcotic and PEG tube usage.
4. Completion of QOL questionnaires.
5. OPTIONAL: Speech and swallowing assessment

5.6.3 Six to Sixty Month (+/- 6 weeks) Assessments

1. Physical examination and weight (kg).
2. Documentation of ECOG performance status.
3. Documentation of narcotic and PEG tube usage.
4. Completion of QOL questionnaires (to occur at 6, 12 and 24 month visits only).
5. CT scan of neck and chest (IV contrast preferred) to be done at 6, 12, 18, 24, and 36 months (+/- 6 weeks) following completion of therapy. CXR (PA and Lateral) may be substituted for CT chest if unable to obtain the latter.
6. OPTIONAL: Speech and swallowing assessment (to occur at 6, 12, and 24 month visits only). These will include MBS at 6 months post-adjuvant therapy, PSS-HN questionnaires at 6, 12, and 24 months, and Fiberoptic Endoscopic Evaluation of Swallowing (FEES) as clinically indicated.

5.6.4 Annual Assessments Subsequently

1. Physical examination and weight (kg).
2. Documentation of ECOG performance status.

5.7 Evaluations for Toxicity and Disease Relapse

All patients who receive any study treatment (starting point of “study treatment” is first dose of post-operative RT) are evaluable for toxicity. Patients are evaluated from first day of study treatment until five years after the conclusion of treatment, or death.

All patients who undergo surgery are evaluable for disease relapse.

5.8 General Concomitant Medication and Supportive Care Guidelines

Primary prophylaxis with G-CSF or Neulasta is not permitted; however it can be used in a non-prophylactic setting following neutropenia. Use of erythropoietin is not permitted.

5.9 Women of Childbearing Potential

Women of childbearing potential (defined as women with regular menses, women with amenorrhea, women with irregular cycles, women using a contraceptive method that precludes withdrawal bleeding, and women who have had a tubal ligation) are required to have a negative serum pregnancy test within 35 days of enrollment.

Female and male patients (along with their female partners) are required to use two forms of acceptable contraception, including one barrier method, during participation in the study and for 1 month following the last day of study treatment.

If a patient is suspected to be pregnant, study treatment should be immediately discontinued. In addition a positive urine test must be confirmed by a serum pregnancy test. If it is confirmed that the patient is not pregnant, the patient may resume dosing.

If a female patient or female partner of a male patient becomes pregnant during therapy or within 1 month after the last day of study treatment, the investigator must be notified in order to facilitate outcome follow-up.

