5.1 Baseline Assessment

The baseline assessment will include the following tests or procedures and must occur within 35 days (PET scan within 42 days) of enrollment:

1. Clinical examination to document extent of primary tumor by laryngoscopy performed in the office or in the operating room (depending on the ease of the exam and the primary tumor site) and palpable involved regional neck nodes.
2. Documentation of site of primary tumor (HPV-related oropharynx or CUP), location and level of clinically involved neck nodes (right or left neck, Level I-V), T stage (1-4), N stage (0-3), and overall clinical stage (I-III by AJCC Cancer Staging Manual Eighth Edition).
3. Documentation of demographic information, including gender (M/F), age (years), height (cm), weight (Kg), and BSA (m²).
4. Documentation of baseline patient symptoms using NCI-CTCAE version 4.0.
5. Documentation of ECOG performance status (Appendix 1).
6. Completion of QOL questionnaires (Appendices 3, 4, 5, 6, and 7).
7. Documentation of Comorbidity Index (Appendix 2).
8. Laboratory evaluations: CBC, CMP, magnesium, PT/PTT, serum pregnancy test if patient is a female of childbearing potential.
9. CT scan of the neck (IV contrast preferred) to document and measure the extent of the primary tumor size and involved regional neck nodes.
10. FDG-PET/CT scan (whole body) to document and measure the FDG avidity at the primary tumor site and at the involved regional neck nodes.
11. OPTIONAL: Speech and swallowing assessment including a modified barium swallow (MBS) study and the Performance Status Scale for Head and Neck Cancer (PSS-HN) questionnaire (Appendix 8).

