5.3 Interim Assessment

The interim assessment will include the following tests or procedures and should occur within 14-42 days of surgery:

1. Clinical examination.
2. Documentation of key data from the pathology report: T (1-4) and N (0-3) stage, ECE status (+/-) and extent of ECE (mm), margin status (+/-).
3. Arm assignment (based on pathology data)
4. Documentation of patient symptoms using NCI-CTCAE version 4.0; please note that AEs considered at least possibly related to surgery need not be recorded.
5. Documentation of ECOG performance status.
6. Completion of QOL questionnaires.
7. Documentation of Comorbidity Index.
8. Laboratory evaluations: CBC, BMP, magnesium, PT/PTT.
9. OPTIONAL: Speech and swallowing assessment including MBS and PSS-HN questionnaire.

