5.4 Postoperative Adjuvant Chemotherapy

5.4.1 ARM 1 ONLY - Cisplatin (one dose) + 21 doses of RT

The dose of cisplatin will be given on the same day as one of the initial 5 doses of POART (refer to Section 5.5 for RT dosing).

Recommended procedures for cisplatin therapy are as follows:

1. Antiemetic premedication prior to cisplatin: palonosetron 0.25 mg IVPB, dexamethasone 10 mg IVPB and aprepitant 150 mg IVPB.
2. Hydration consisting of 1L IVF NS (10 meq KCL/L + 8 meq MgSO₄/L) over 60 minutes before and after cisplatin on the day of dosing. 2L IVF NS over 60 minutes on each of the two days following cisplatin dosing.
3. Administration of cisplatin (100 mg/m² IVPB over 60 minutes) on one day only during one of the first 5 doses of radiation.
4. Physical examination will be performed on the day of cisplatin administration and on day 22 (+/- 2) and 36 (+/- 2) after starting radiation therapy.
5. Weight (kg) will be collected weekly during radiation.
6. Documentation of ECOG performance status will be done on the day of cisplatin administration and on days 22 (+/- 2) and 36 (+/- 2) after starting radiation therapy.
7. Documentation of patient symptoms using NCI-CTCAE version 4.0 will be done on the day of cisplatin administration and on days 22 (+/- 2) and 36 (+/- 2) after starting radiation therapy.
8. CBC, BMP and magnesium on the day of cisplatin administration and on days 22 (+/- 2) and 36 (+/- 2) after starting radiation therapy.
9. Patient to complete QOL questionnaire prior to starting radiation (-7/+0) and during the fourth week of radiation (radiation doses 16-21) and 36 (+/- 2) days after starting radiation therapy.
10. OPTIONAL: Patient to receive speech and swallowing assessments prior to starting radiation* and during the fourth week of radiation (radiation doses 16-21) and 2 weeks after completing radiation therapy.
*Modified barium swallow not needed within one week prior to starting radiation.

5.4.2 ARM 2: No Cisplatin. 21 doses of RT only.

Refer to Section 5.5 for RT dosing instructions.

1. Physical examination and weight (kg) will be performed on the first day of radiation therapy and on days 22 (+/- 2) and 36 (+/- 2) after starting radiation therapy.
2. Weight (kg) will be collected weekly during radiation.

3. Documentation of ECOG performance status will be done on the first day of radiation therapy and on days 22 (+/- 2) and 36 (+/- 2) after starting radiation therapy.

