5.5 POART

It is recommended that radiation therapy begin within 28 to 49 days (and no later than 56 days) after the surgical resection. Intensity modulated radiation therapy (IMRT) or intensity modulated proton therapy (IMPT) is to be used exclusively for this study. IMRT or IMPT will be delivered once per day Monday through Friday per routine clinical practice in Arm 3. In Arms 1 and 2, one BID treatment will be given during the course of therapy. If patient logistics prohibit the one BID treatment, once daily treatments throughout will be acceptable. The total dose to the postoperative tumor bed will be:

- Arm 1: 4200 cGy in 21 fractions of 200 cGy each over 4 weeks
- Arm 2: 4200 cGy in 21 fractions of 200 cGy each over 4 weeks
- Arm 3: 6000 cGy in 30 fractions of 200 cGy each over 6 weeks

Additional regions in the ipsilateral and contralateral neck at risk for microscopic disease in the cervical lymph nodes will receive:

- Arm 1: 3780 cGy in 21 fractions of 180 cGy each
- Arm 2: 3780 cGy in 21 fractions of 180 cGy each
- Arm 3: 5200 cGy in 30 fractions of 173 cGy each

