14.0 STUDY CALENDARS

14.1 Baseline and Treatment Calendar

	Baseline ⁴	Surgery	Interim Assessment (14 to 42 days post-surgery)	Post-operative Adjuvant Chemotherapy/Radiation		
				D1	D2 ¹²	D36 ¹²
Informed consent	X					
Laryngoscopy ¹	X					
PE w/ECOG PS	X		X	X	X	X
Weight	X			X ⁸		X ⁸
Comorbidity index	X		X			
CBC	X		X	X	X	X
CMP + magnesium	X					
BMP + magnesium			X	X	X	X
PT/PTT	X		X			
Pregnancy test ²	X					
Neck CT w/contrast	X					
FDG-PET/CT	X					
QOLs ³	X		X	X ¹³	X	X
OPTIONAL: Speech & Swallow Study ¹⁰	X		X	X ¹¹	X	X ⁹
Surgery ⁵		X ⁵				
Rad Tx Planning			X			
IMRT or IMPT ⁶				X		X ⁹
Arms 1 & 3: Cisplatin ⁷				X ⁷	X ⁹	X ⁹
AE assessment	X		X	X	X	X
Documentation of narcotic usage				X	X	X

1. Assessment of primary tumor site will be done by laryngoscopy performed in the office or operating room.

2. In women of childbearing potential only.

3. FACT H&N, M.D. Anderson Dysphagia Inventory, University of Michigan Xerostomia Index, Scale of Subjective Total Taste Acuity, and Neck Dissection Impairment Index.

4. Baseline assessments must take place no more than 35 days prior to enrollment, with the exception of PET scans (within 42 days).

5. See Section 5.2.

6. Arms 1 and 2: Once daily M-F, with one BID treatment each week for 4200 cGy in 21 fractions. Arm 3: Once daily M-F for 6000 cGy in 30 fractions

7. To be given during initial 5 doses of POART. See Section 5.4.1 for fluids and premedications. On Arm 3, cisplatin will only be given to patients with pathologic evidence of positive margins or ECE (see section 1.9).

8. Collect weight weekly during Radiation.

9. Arm 3 only.

10. Modified barium swallow and the Performance Status Scale for Head and Neck Cancer (PSS-HN) questionnaire.

11. Modified barium swallow NOT needed on this day.

12. Arm 1 & 2 +/- 2 days; Arm 3 +/- 5 days

13. -7/+0 days

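### The only scheduled pregnancy test precedes surgery: it is about 28 days old at best, and 91 days or more at worst, when radiation starts, and no repeat is required

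*Combined protocol and SAP*

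**What the plan says.** The pregnancy test appears in four places, all at screening or Baseline:

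- Section 5.9 says that women of childbearing potential "are required to have a negative serum pregnancy test within 35 days of enrollment".
- Section 5.1, item 8, includes among the baseline laboratory tests a "serum pregnancy test if patient is a female of childbearing potential".
- Exclusion criterion 7 (section 3.2) asks for a negative result at screening and accepts serum or urine.
- The calendar in section 14.1 marks the test in the Baseline column only. Its footnote 4 gives the direction of the window: "Baseline assessments must take place no more than 35 days prior to enrollment" (PET scans have 42 days).

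Treatment comes later. Section 5.5 recommends that "radiation therapy begin within 28 to 49 days (and no later than 56 days) after the surgical resection". For Arm 1, section 5.4.1 says: "The dose of cisplatin will be given on the same day as one of the initial 5 doses of POART". Section 5.7 takes the first post-operative radiation dose as the start of study treatment.

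The laboratory lists after surgery contain no pregnancy test. Section 5.3 has "Laboratory evaluations: CBC, BMP, magnesium, PT/PTT". Section 5.4.1 has "CBC, BMP and magnesium on the day of cisplatin administration" and again on days 22 and 36. Arms 2 and 3 repeat the same three items on their own schedules.

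**The concern.** The test is anchored to enrolment, while the exposure that matters to a fetus, radiation and in many patients cisplatin at 100 mg/m², begins weeks to months later. A site that follows every instruction can start both on a result one to three months old or older.

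The protocol itself treats such exposure as unacceptable: section 5.9 stops treatment at once on suspicion of pregnancy, and section 5.10 lists suspected pregnancy among the reasons for discontinuation. The blood count, chemistry and even the coagulation tests are repeated after surgery, but the pregnancy test is not.

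A lesser point of wording goes with this. The eligibility text is looser than the on-study rule. Inclusion 6 can be read as accepting a single method or abstinence, whereas section 5.9 asks for two forms including a barrier and does not mention abstinence. Exclusion 7 accepts urine, whereas sections 5.1 and 5.9 specify serum. A site can satisfy both sets by following the stricter one, so this is a matter of tidiness.

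**Working it through.** The documents state no age for the test at the start of radiation, so there is no figure to reproduce. The age follows from adding the windows.

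**Inputs**

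- Test to enrolment: 0 to 35 days (sections 5.9 and 14.1, footnote 4).
- Enrolment to surgery: E days, E ≥ 0. Inclusion 2 refers to a resection still to come, and section 4.0 bars any protocol intervention before registration. No upper limit is given.
- Surgery to radiation: 28 to 49 days recommended, 56 at the latest (section 5.5).
- Arm 1 cisplatin: with any one of radiation doses 1 to 5 (section 5.4.1).

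**Formula**

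Age at first radiation dose = (test to enrolment) + E + (surgery to radiation).

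**Results (days)**

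| Case | Calculation | Age |
|---|---|---|
| Newest test, recommended window | 0 + E + 28 to 0 + E + 49 | 28 to 49, plus E |
| Newest test, latest start | 0 + E + 56 | 56 + E |
| Oldest test, recommended window | 35 + E + 28 to 35 + E + 49 | 63 to 84, plus E |
| Oldest test, latest start | 35 + E + 56 | 91 + E |

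The smallest value, 28 days, takes E = 0. It rests on a recommended earliest start, not a hard limit, hence about 28.

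**Cisplatin in Arm 1.** With once-daily weekday treatment, dose 5 falls 4 calendar days after a Monday start and 6 after a start on any other weekday. The latest case is 91 + 6 = 97 days, plus E.

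**Effect of E.** The documents give no value. If E is assumed to be 14 to 28 days, the maximum at first radiation is 91 + 14 = 105 to 91 + 28 = 119 days.

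**Could an existing draw fill the gap?** The interim visit is 14 to 42 days after surgery. A test added there on day 14, with radiation on day 56, would be 56 − 14 = 42 days old, so moving the test to that visit is not enough by itself. In Arm 1 the section 5.4.1 draw is tied to the cisplatin day, which can fall after radiation has started. In Arm 3 the section 5.4.3 draws are tied to cisplatin days, and patients without positive margins or extracapsular extension receive no cisplatin; for them only the Day 1 column of the calendar shows a draw. The routine preoperative laboratory work in section 5.2 does not name a pregnancy test, and one done then would still be about 28 days old or more at radiation.

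**The case against.** The best defence is that the test is one safeguard among several. Section 5.9 requires two forms of contraception during participation and for a month after treatment. Inclusion 6 obliges the patient to report a suspected pregnancy immediately. Treatment stops on suspicion alone, and clinical visits are scheduled around the start of adjuvant therapy. What remains is an unnoticed conception despite contraception, in a subgroup of unstated size. This lowers the probability and is the main reason the point ranks low. It does not remove the gap, because none of these measures verifies status before the first dose. The trigger of suspicion is also weakest in women with amenorrhea or irregular cycles, whom section 5.9 expressly counts as of childbearing potential.

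It can also be said that the start of study treatment in section 5.7 serves a rule about evaluability, and that section 5.10 counts surgery as part of treatment, so the test does precede the first element of therapy. That is a fair reading, but it does not change the age of the result when radiation and cisplatin begin.

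The 91-day figure combines the earliest permitted test with the latest permitted radiation start, and the 105 to 119 days rest on an assumed interval. Both are upper ends, not typical values. Even the newest test in the recommended window is 28 to 49 days old.

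Finally, a 7-day window is a judgement: the protocol uses that window for a questionnaire, not for safety testing. This is accepted; the precedent shows only that the window is workable.

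**Conclusion.** The concern holds. As written, the plan lets radiation and cisplatin start on a pregnancy test that is about 28 days old at best and 91 days old, plus the enrolment-to-surgery interval, at worst; for Arm 1 cisplatin the upper end is 97 days plus that interval. These figures rest only on the stated windows and on once-daily weekday treatment for the cisplatin case. The 105 to 119 days additionally assume 14 to 28 days from enrolment to surgery.

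The weight is low. Only women of childbearing potential are affected. The documents do not give their number; that it is small is a presumption. This is a cheap safety improvement with no bearing on the trial's statistical conclusions.

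**What to change.** For women of childbearing potential in all three arms, require a negative serum pregnancy test within 7 days before the first radiation dose, with the result known before any radiation or cisplatin is given. Name the first radiation dose as the anchor, not the cisplatin day. Keep the Baseline test. Enter the requirement in sections 5.3 and 5.4, in section 5.9 and in the calendar in section 14.1. The window matches the -7/+0 days already used for the Day 1 quality-of-life questionnaires. An interim draw may serve if it falls inside that window. The test would then be at most 7 days old at first radiation and at most 7 + 6 = 13 days old at the latest Arm 1 cisplatin dose.

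In the same edit, bring inclusion 6 into line with section 5.9, stating whether abstinence is acceptable, and bring exclusion 7 into line with the serum test in sections 5.1 and 5.9.

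The cost is one serum assay for each woman concerned, plus changes to the protocol, the eligibility checklist and, where needed, the consent text. The assay can share a scheduled draw when that draw falls in the window and precedes radiation; otherwise a separate sample is needed.

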5.10 Duration of Therapy

If at any time the constraints of this protocol are considered to be detrimental to the patient’s health and/or the patient no longer wishes to continue protocol therapy, the protocol therapy should be discontinued and the reason(s) for discontinuation documented in the case report forms.

In the absence of treatment delays due to adverse events, treatment may continue for the duration of surgery and RT +/- cisplatin until one of the following criteria applies:

- Documented and confirmed disease progression
- Death
- Adverse event(s) that, in the judgment of the investigator, may cause severe or permanent harm or which rule out continuation of study drug
- General or specific changes in the patient's condition render the patient unacceptable for further treatment in the judgment of the investigator
- Suspected pregnancy
- Serious non-compliance with the study protocol
- Lost to follow-up
- Patient withdraws consent
- Investigator removes the patient from study
- The Siteman Cancer Center decides to close the study

Patients who prematurely discontinue treatment for any reason will be followed as indicated in the study calendar.

6.0 PHARMACEUTICAL INFORMATION

6.1 Cisplatin (CDDP, Platinol-AQ®)

6.1.1 Cisplatin Description

Molecular formula: PtCl₂H₆N₂

Molecular weight: 300.1.

6.1.2 Clinical Pharmacology

The mechanism of action of cisplatin has not been clearly elucidated. However the most likely mechanism of antitumor action of this drug resides in its ability to inhibit DNA synthesis, and to a lesser degree, RNA and protein synthesis. It has also been shown that Cisplatin binds to DNA and produces inter-strand cross-links. Also cisplatin is not phase-sensitive and its cytotoxicity is similar in all phases of the cell cycle. Additional information can be found in the package insert.

6.1.3 Supplier

Cisplatin is commercially available as 1 mg/mL in both 50 mL multiple dose vial and 100 mL multiple dose vial.

6.1.4 Dosage Form and Preparation

The stability of cisplatin in solution is dependent upon the chloride ion concentration present in the diluent. Cisplatin should be diluted into an IV solution containing NaCl at a minimum chloride ion concentration of 0.040

mol/L (0.2% NaCL). Needles, syringes, catheters and IV administrations sets containing aluminum must be avoided during preparation and administration due to cisplatin-aluminum reaction causing precipitation and loss of potency. Mannitol 12.5 to 25 gm may be added per institutional guidelines.

6.1.5 Storage and Stability

The dry, unopened vials should be stored at room temperature (15° -25° C). The unopened container should be protected from light and stored in the carton until contents are used. Do not refrigerate. Cisplatin remaining in the amber vial following initial entry is stable for 28 days protected from light or for 7 days under fluorescent room light.

6.1.6 Administration

Patients will receive cisplatin via IV infusion over 60 minutes. Adequate hydration must be maintained during and after administration as described in the treatment section. It is recommended that all patients should be premedicated with antiemetics.

7.0 DOSE MODIFICATIONS

At each of the scheduled visits noted in the study calendar, an assessment of adverse events (AEs) will be made by the treating physician with toxicity grading using the NCI CTCAE version 4. Patients without AEs will continue on study treatment as planned. Patients who develop grade 1-2 or selected grade 3 (nausea/vomiting/fatigue) AEs will be supported symptomatically and encouraged to continue on study treatment as planned. Modifications in their therapy may be necessary and will be detailed below. Management of specific AEs is noted below.

